Project BA2023

study protocol and statistical analysis

plan

Title: Analyses of Anemia Risk Factors and Prognosis in VLBW Infants.

Study center

Shenzhen Bao'an Women's and Children's Hospital (ShenzhenBMCHH)

Shenzhen Longhua Women's and Children's Hospital

Time frame

Study Start: March 1, 2023

Study Completion: March 24, 2024

1. Background

Preterm infants (accounts for 9.9% of newborn infants in 2020) are born with immature organs and immune system[1]. Especially, 4% of them are extremely preterm infants with a gestational age of less than 28 weeks[2]. In recent years, the treatment and management of extremely preterm infants has become the main task of NICU. Moreover, the morbidity rate for extremely premature infants around the world has been rising annually. These vulnerable patients are prone to various complications. Anemia is one of the most common complications that occur during hospitalization in these infants[3]. Therefore, According to a survey by the Canadian Neonatal Network (CNN), over 75% of extremely preterm infants receive at least one blood transfusion treatment during hospitalization[4], and WhyteRK et al.[5] even pointed out that over 90% of extremely preterm infants require blood transfusion treatment during hospitalization. Most of the recipients of blood transfusions are caused by anemia, indicating a very high incidence and severity of anemia in these immature infants. Anemia of prematurity (AOP) can cause a series of adverse consequences such as apnoea, prolonged mechanical ventilation, prolonged hospital stay, necrotizing enterocolitis (NEC) [6], retinopathy of prematurity (ROP) [7], infection, and extrauterine growth restriction (EUGR). It can be seen that anemia in premature infants, especially in extremely preterm infants, has a significant impact on their prognosis.

There is a lack of evidence regarding the relationship between blood hemoglobin level at birth and the neonatal morbidity and mortality of preterm infants despite the mode of delivery and prenatal infection. It remains unknown the impact of early anemia on the neonatal morbidity and mortality of extremely preterm infants[8]. With this study, We hope to demonstrate the relationship between anemia on admission to the neonatal intensive care unit (NICU) and the neonatal morbidity and mortality in extremely preterm infants.

2. Objective and hypotheses

Objective: To study the risk factors of anemia in different stages of extremely preterm infants and their impact on prognosis, which provide a certain evidence for improving the prognosis of these infants.

Hypothesis: Small gestational age and low birth weight are risk factors for anemia and receiving blood transfusion treatment in extremely preterm infants. The younger the gestational age and the lower the birth weight, the more severe the anemia, and the greater the likelihood of receiving blood transfusion treatment.

3. Study design

3.1. study subject

From January 1, 2020 to December 31, 2022, extremely preterm infants with a gestational age of less than 28 weeks were admitted to Bao'an Women's and Children's Hospital affiliated with Jinan University and Longhua District Women's and Children's Hospital.

3.2. The method of study

This was a retrospective study on the maternal and infant clinical and electronic records. We analyzed the maternal and obstetrical data, demographics, as well as the neonatal morbidity and mortality diagnosed during hospitalization. The study was approved by the Ethics Committee of our institution.

3.3. Inclusion criteria

Extremely preterm infants with admission age \leq 24 hours, hospital stay \geq 14 days, and gestational age less than 28 weeks were included.

Anemia of Premature (AOP):

- Within 2 weeks of birth, venous blood hemoglobin level (Hb) \leq 130g/L, capillary blood \leq 145g/L.
- Age 2 weeks to 1 month, Hb $<$ 110g/L.
- Age after one month, Hb $<$ 90g/L.

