3.4. Exclusion criteria

- (1) Transfer or automatic discharge within 2 weeks.
- (2) Patients with combined neonatal hemorrhagic diseases.
- (3) Newborns with severe malformations (such as congenital diaphragmatic hernia, umbilical protrusion, multiple malformations, etc.) or chromosomal abnormalities.
- (4) Incomplete and inaccurate hospitalization data.

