3.5. General information

Several variables on mother, pregnancy, delivery, resuscitation, hematologic parameters including the Hct and Hb at admission, PRBC transfusions, use of vasopressor agents within the first 72 h of life, data on invasive and noninvasive respiratory support, neonatal morbidity and mortality, and length of NICU stay were collected and analyzed.

Care practices included antenatal steroid use, the use of antenatal magnesium sulfate, cesarean section, and delivery room resuscitation.

- Antenatal steroids: A full cycle of antenatal steroids was considered when at least 12 h had elapsed after the last dose of dexamethasone (four doses of 6 mg of dexamethasone given intramuscularly 12 h apart) administered to the mother [9].
- Antenatal magnesium sulfate was defined as the intravenous administration of magnesium sulfate to the mother during pregnancy at any time before delivery.
- Gestational age (GA) was determined according to the first day of the last menstrual period, an early prenatal ultrasound examination, and a physical examination of the infant after birth [10].
- Maternal chorioamnionitis was diagnosed clinically during pregnancy, labor, or delivery.
- Small for gestational age (SGA) was defined as a birth weight below the 10th percentile, based on the Fenton Growth Chart [11].
- Neonatal sepsis was diagnosed in the presence of clinical signs (fever; hypothermia; lethargy; tachypnea; apnea/bradycardia; cyanosis; and hypoglycemia not explained by other diagnosis), associated to at least two laboratory markers (thrombocytopenia; leukocytosis or leucopenia; C-reactive protein elevation; PCT; I/T) according to our National Program of Infection Control Guidelines [12]. Early-onset sepsis and late-onset sepsis were considered if diagnosed before and after the first 72 h of life, respectively.
- Intraventricular hemorrhage (IVH) was classified according to Volpe [13].

- Bronchopulmonary dysplasia (BPD) was defined according to the National Institute of Health [14]. For the analysis of this study, we considered BPD as the dependency for oxygen until 36 weeks of corrected age.
- Parenteral nutrition was used as soon as there was clinical stability, preferably since day one of life, starting with a volume of 70 ml/kg/day, with daily increments until 150 mg/kg/day by day seven of life. Incubator humidity is usually 70% during the first week.

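### The 14-day minimum stay excludes every early in-hospital death, so the cohort cannot estimate how admission anemia relates to mortality from admission

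*Combined protocol and SAP*

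**What the plan says.** - **Entry.** Section 3.3 requires admission at no more than 24 hours of age and a stay of at least "14 days, and gestational age less than 28 weeks were included". Early death is not exempted.
- **Other early exits.** Section 3.4, item (1), separately excludes "Transfer or automatic discharge within 2 weeks". Death is not mentioned.
- **Aim.** Section 1 ends with the hope of showing the relationship between "anemia on admission to the neonatal intensive care unit (NICU) and the neonatal morbidity and mortality in extremely preterm infants". The formal objective in section 2 is broader: "To study the risk factors of anemia in different stages of extremely preterm infants and their impact on prognosis".
- **Exposure.** Section 3.5 collects "hematologic parameters including the Hct and Hb at admission".
- **Outcomes.** Section 3.2 analyses "neonatal morbidity and mortality diagnosed during hospitalization". Table 1 in section 3.6 lists death, early-onset sepsis and IVH among the morbidity and mortality endpoints. On sepsis, section 3.5 says "Early-onset sepsis and late-onset sepsis were considered if diagnosed before and after the first 72 h of life, respectively".
- **Analysis.** Section 4 gives no time origin, no landmark and no handling of early deaths. No section limits the mortality aim to infants who reached day 14.

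**The concern.** The exposure is fixed at admission, but entry to the cohort depends on an event about two weeks later that the exposure may itself influence. Deaths in the first two weeks are part of the outcome named in section 1, and the entry rule removes them. The result would be read as applying to extremely preterm infants from admission, while only later deaths were counted. A null or reversed association could be taken as evidence that admission anemia is harmless. No regression on the retained infants can recover the excluded deaths.

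Early morbidity is affected in the same way. Early-onset sepsis is diagnosed before 72 hours, so an affected infant is counted only after surviving about 11 more days (14 − 3). Infants with IVH who die early are lost as well.

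The rule does suit the two later anemia windows in section 3.3 (2 weeks to 1 month, and after one month). The difficulty is that one undeclared cohort serves those windows and the admission analysis alike.

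**Working it through.** **Logic.** Admission at age 0 to 1 day plus a stay of at least 14 days means alive and in hospital at about 14 to 15 days of age. Deaths in the cohort can occur only after that. What can be estimated is in-hospital death given survival and continued stay to about day 14.

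**Inputs.** The documents give no sample size, anemia prevalence, death rate or timing of death, so there is no figure of the plan's own to reproduce. All rates below are assumptions for illustration: 200 infants, 30% anemic at admission (60 anemic, 140 not).

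**Distortion.** Let *e* be the risk of death before day 14 and *l* the risk afterwards among those remaining. Risk from admission is *e* + (1 − *e*)*l*; risk in the plan's cohort is *l*. Each pair is anemic vs not anemic.

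| Case | *e* | *l* | Risk from admission | RR from admission | RR in plan's cohort | Deaths removed |
|---|---|---|---|---|---|---|
| A | 20% vs 10% | 5% vs 5% | 0.240 vs 0.145 | 1.66 | 1.00 | 26.0/34.7 = 75% |
| B | 25% vs 10% | 8% vs 10% | 0.310 vs 0.190 | 1.63 | 0.80 | 29.0/45.2 = 64% |
| C | 10% vs 10% | 16% vs 8% | 0.244 vs 0.172 | 1.42 | 2.00 | 20.0/38.7 = 52% |

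For case A, anemic infants: 0.20 + 0.80 × 0.05 = 0.240. Early deaths: 60 × 0.20 + 140 × 0.10 = 26.0. All deaths: 60 × 0.240 + 140 × 0.145 = 34.7.

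**Precision when the odds ratio is not distorted.** Suppose total mortality *d* is 30% vs 15% and the same share *f* of deaths is early in both groups. The retained odds are *d*(1 − *f*)/(1 − *d*), so (1 − *f*) cancels and the OR is (0.30/0.70)/(0.15/0.85) = 2.43 for every *f*. Intervals are Woolf intervals from expected counts. Power is the two-proportion normal approximation with pooled null variance, two-sided 0.05. Both are rough at the smallest event count.

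| Early share | Expected deaths kept | 95% CI for OR | Power |
|---|---|---|---|
| 0 (all deaths counted) | 39 | 1.18–5.00 | 68% |
| 50% | 20 | 0.93–6.33 | 46% |
| 65% | 14 | 0.79–7.45 | 38% |
| 80% | 8 | 0.57–10.4 | 27% |

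**Early-onset sepsis.** Assume 10% of admissions have it, early death is *x* with it and 10% without. The proportion observed in the cohort is 0.1(1 − *x*)/[0.1(1 − *x*) + 0.9 × 0.9]: 9.0%, 8.0% and 6.9% for *x* = 20%, 30% and 40%.

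**Early transfers once early deaths are restored.** With 10% transferred in each group (6 and 14 infants), 54 and 126 are observed, with 16.2 and 18.9 deaths.
- All anemic transfers die, no others: (22.2/37.8)/(18.9/121.1) = 3.76.
- The reverse: (16.2/43.8)/(32.9/107.1) = 1.20.
- Transfers coded as event-free, 15% vs 5% transferred: (15.3/44.7)/(19.95/120.05) = 2.06.
- Transfers coded as event-free, 5% vs 15% transferred: (17.1/42.9)/(17.85/122.15) = 2.73.

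The undistorted value is 2.43 throughout.

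**The case against.** The strongest reply is about scope. The formal objective speaks only of prognosis, the single hypothesis concerns gestational age, birth weight, anemia and transfusion, and the only multivariable model in section 4 is for morbidities. The mortality aim is a sentence in the Background, and death is one of eight unranked endpoints. This stands as a limit: the defect concerns the mortality and early-morbidity questions, not every aim. It does not remove the conflict, because the aim is stated and death is listed.

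The 14-day rule may also have been meant only for infants who left early, since section 3.4 names transfer and discharge but not death. That is possible, but those infants already have their own exclusion, and the stay criterion as written has no exception for death. If early deaths were meant to be included, the text still needs correcting.

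A 14-day cohort is legitimate when declared as a landmark, and each cohort ratio in the first table is correct for death after day 14 among infants still in hospital. This stands too. The error is that the plan neither declares the landmark nor restricts the aim, so the ratio would be read from admission.

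The figures are all assumed, and an equal early share protects the odds ratio only. In the precision scenario the risk ratio moves from 2.00 (0.30/0.15) to 2.18 at a 50% early share: (9/51)/(10.5/129.5). The conclusion rests on the entry rule and not on these numbers.

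**Conclusion.** The concern holds and must be fixed. Followed as written, the plan answers a different question from the one in section 1: in-hospital death after about day 14 among infants alive and still hospitalized then, instead of death from admission.

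Neither the size nor the direction of the distortion can be derived from the documents. Under the assumed rates the association can be hidden, reversed or exaggerated. If the early share of deaths is the same in both groups, the odds ratio is unchanged and the loss is one of precision, with power falling from 68% to between 46% and 27%.

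That early deaths are excluded follows from the text alone. The magnitudes depend wholly on the assumptions stated.

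**What to change.** 1. **Admission-anemia analyses of death and early morbidity.** Replace the stay rule with: all otherwise eligible infants under 28 weeks admitted at 24 hours of age or less, irrespective of length of stay; in-hospital death at any time is an event. State that a short chart caused by early death is not in itself incomplete data under exclusion (4), or early deaths could be dropped again.
2. **Infants transferred or discharged within 2 weeks.** Do not code them as event-free. Either keep exclusion (1), report their number by admission-anemia status and add a best/worst-case sensitivity analysis, or use a time-to-event analysis that censors them, stating the assumption that leaving is non-informative.
3. **Later anemia windows.** Keep the 14-day cohort as a declared landmark cohort, requiring infants to be alive and in hospital at the start of each window, and state that results are conditional on this.
4. **If early-death records cannot be added.** Restate the mortality aim as in-hospital death after day 14 among infants alive and still hospitalized then, and report the excluded early deaths by admission-anemia status.

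A secondary and separable addition concerns BPD, for which section 3.5 says "we considered BPD as the dependency for oxygen until 36 weeks of corrected age". Death before 36 weeks competes with that outcome, so define its denominator and report BPD or death before 36 weeks beside it.

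The cost is revised wording plus abstraction of early-death charts from the same two hospitals and dates, with no new procedures or enrolment. Item 4 needs only a count and a restated aim. Early transfers will leave some uncertainty.

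### The SAP does not say which anemia exposure enters the prognosis analysis; if the age-window definition is used, early-onset sepsis and other outcomes can precede the anemia they are tested against

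*Combined protocol and SAP*

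**What the plan says.** Two exposures are offered for the prognosis question.

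- Section 1 (Background) says the study hopes to relate "anemia on admission to the neonatal intensive care unit (NICU) and the neonatal morbidity and mortality in extremely preterm infants". Section 3.5 lists Hb and Hct at admission among the data collected, and section 3.3 requires admission within 24 h of birth.
- Section 2 gives the objective as the "risk factors of anemia in different stages of extremely preterm infants and their impact on prognosis". Section 3.3 defines anemia of prematurity (AOP) only by age: window 1 ("Within 2 weeks of birth, venous blood hemoglobin level (Hb"), window 2 (two weeks to one month) and window 3 ("Age after one month, Hb"), which has no upper limit. The Background uses the same term when it lists consequences: "Anemia of prematurity (AOP) can cause a series of adverse consequences such as apnoea, prolonged mechanical ventilation, prolonged hospital stay, necrotizing enterocolitis (NEC", followed by ROP, infection and EUGR.

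Outcomes are "the neonatal morbidity and mortality diagnosed during hospitalization" (section 3.2). Section 3.5 separates early-onset from late-onset sepsis at 72 h and ties BPD to 36 weeks corrected age. Table 1 lists EOS under both General information and Neonatal morbidity and mortality.

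Section 4 has group comparisons and one sentence on logistic regression for predictors of morbidity. It names no anemia variable, no time point and no rule on the order of anemia and outcome.

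**The concern.** A prognostic claim needs the exposure to be fixed before the outcome can occur. Admission Hb comes close to that. AOP by window does not, because an infant can become anemic at any time in a window, while the outcome may be diagnosed at any time in the stay.

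Two errors follow if the windows are used for prognosis. A complication that came first can be reported as a consequence of the anemia. And for death, an infant who dies early has less time in which to be classed as anemic, so anemia can look protective when it has no effect. Adjusting for gestational age cures neither, because both come from timing.

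**Working it through.** The plan gives no sample size, prevalence, onset time or effect size, so there is no figure of its own to reproduce.

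**Order, from the documents' own limits**

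- EOS closes at 72 h = day 3. Window 1: (14 − 3)/14 = 11/14 = 79% of calendar days come after it. Windows 2 and 3: all days. The 79% counts days, not Hb samples or infants.
- IVH, NEC, ROP and EUGR have no onset time in the documents, and late-onset sepsis has only a lower limit (72 h). Each may come before or after the qualifying Hb.
- Death: the stay of at least 14 days puts every in-hospital death at or after the end of window 1. It is not ordered against windows 2 and 3.
- BPD: the latest eligible birth is 27 weeks 6 days, so 36 weeks is at least 36×7 − (27×7 + 6) = 252 − 195 = 57 days after birth. That is after windows 1 and 2, but not necessarily after window 3.

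**Size for EOS and window 1 (all rates assumed, no effect of anemia)**

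Take a constant anemia hazard with 50% anemic by day 14, λ = ln 2/14 = 0.0495 per day, multiplied by HR after day 3 in infants with EOS. Then P(anemic | EOS) = 1 − exp[−λ(3 + 11·HR)], and P(anemic | no EOS) = 0.5, so its odds are 1.

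| HR | P(anemic given EOS) | Spurious OR |
|---|---|---|
| 0.5 | 0.344 | 0.52 |
| 0.7 | 0.411 | 0.70 |
| 1.5 | 0.619 | 1.63 |
| 2 | 0.710 | 2.45 |
| 3 | 0.832 | 4.94 |

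HR above 1 means that sepsis promotes later anemia; HR below 1 means that it leads to transfusion that raises later Hb. The documents do not say which prevails.

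Not all window-1 anemia follows EOS. Under a constant hazard with 20/40/60% anemic by day 14, the share of cases arising by day 3 is [1 − (1 − p)^(3/14)]/p = 23/26/30%.

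**Other morbidities (simulated; adjusted for gestational age; 40% anemic by day 14, prevalence 30%, no true effect)**

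- Onset spread over days 0-30: OR 1.16/1.28/1.53 for HR 1.5/2/3, and 0.83-0.91 for HR 0.5-0.7.
- Onset spread over days 0-60: OR 1.06/1.14/1.25 for HR 1.5/2/3. Over the wider grid of assumed rates, rejection at an assumed N of 200 was 4-10% against a nominal 5%, so the effect is small here.

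**Death and later windows (rates assumed, no effect of anemia)**

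Let p be the proportion anemic over the full window, with constant hazard. An infant who dies at a uniformly distributed time inside the window is recorded as anemic with probability m = 1 − p/[−ln(1 − p)], which is 0.104/0.217/0.345 for p = 0.2/0.4/0.6.

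- Window 2 (days 14-30), deaths over days 14-60: P(anemic | died) = (16/46)m + (30/46)p = 0.167/0.336/0.511. Dividing the odds by p/(1 − p) gives OR 0.80/0.76/0.70.
- Window 2, deaths over days 14-30: P(anemic | died) = m, OR 0.46/0.42/0.35.
- Window 3 (taken as days 30-90), deaths over days 14-90: P(anemic | died) = (60/76)m, OR 0.36/0.31/0.25.

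**With the order fixed (simulated, same assumptions)**

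A day-14 landmark gave OR 0.97-1.03 for morbidities. A one-month landmark gave 0.95-1.03 for morbidities and 0.99-1.02 for death.

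**The case against.** The strongest reply is that the documents lean toward admission anemia. The Background sentence stating what the study hopes to show names it, admission is the only timed Hb listed among the collected data, and the hypotheses in section 2 concern risk factors for anemia and transfusion only. On that reading the windows serve the risk-factor aim, EOS may properly be a risk factor in one analysis and an outcome in another, and listing it twice is not in itself an error. This is a fair reading and it removes most of the problem. But the Objective also speaks of impact on prognosis, the only anemia definition is the windows, and section 4 adopts neither.

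A reader might go further than the documents allow in four ways.

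- *That the same gap remains with admission Hb, because 24 of the 72 EOS hours may pass before admission.* Section 3.2 analyses morbidity diagnosed during hospitalization, so EOS diagnosed before admission is not counted. Only the interval between admission and the Hb sample is open.
- *That EOS always precedes the anemia.* This is certain for windows 2 and 3 only; window 1 starts at birth.
- *That no outcome is ordered after the anemia.* Death is ordered after window 1, and BPD assessment after windows 1 and 2. Early lung disease may still affect both anemia and BPD, but that is confounding.
- *That morbidity ORs are inflated.* The direction depends on whether the complication lowers later Hb or leads to transfusion that raises it.

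It can also be said that landmarks are heavy machinery for a small retrospective study. That stands for window 3, where too few outcomes may remain.

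**Conclusion.** The concern holds in conditional form. The SAP does not choose between admission anemia and window anemia as the prognostic exposure. As written it allows EOS to be tested as an outcome of anemia that, in windows 2 and 3, can only be recorded later. That much follows from the documents alone.

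The remaining sizes rest on assumed rates. For death against window-2 or window-3 anemia the bias is below 1 under the null, from mild (0.70-0.80) to strong (0.25-0.46) depending on when deaths fall. For EOS against window-1 anemia the OR ranged from about 0.5 to 4.9. For morbidities with later onset it was smaller, and close to 1 when onset is spread over 60 days. None of these figures estimates the bias in this study; they show that it can be material. This should be fixed before any prognostic result is interpreted. Confidence is medium, because admission anemia may be what the investigators intend.

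**What to change.** - **Main analysis.** State in section 4 that admission Hb is the exposure for prognosis, and count outcomes, EOS included, diagnosed after that sample.
- **Stage-specific anemia, if it is also related to prognosis.** Use landmarks common to anemic and non-anemic infants: day 14 for window 1 and one month for window 2. Classify anemia by Hb up to the landmark, include infants alive, in hospital and free of that outcome at that age, and count only later outcomes. Do not use window-3 anemia as a prognostic exposure unless a stated later landmark leaves enough outcomes.
- **EOS.** One role per model: outcome only in admission-anemia models, risk factor or covariate in later-anemia models. Amend Table 1 to match.
- **Missing dates.** Report an association without direction.

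The wording costs little, and admission Hb is already collected. Hb sample dates and diagnosis dates must be taken from the existing records; the documents do not say that this was done. Fewer outcomes count after later landmarks. With onsets spread evenly over days 0-30, 14/30 = 47% fall before day 14. Over days 0-60, 14/60 = 23% fall before day 14 and 30/60 = 50% before day 30. Of deaths spread over days 14-90, 16/76 = 21% fall before day 30.
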